#### 4.9.3 Analysis of DLTs

Dose Limiting Toxicities (DLTs) will be assessed for each subject in the Dose Escalation portion during the 21 days following their first PEGPH20 dose. Number and percent of subjects experiencing DLTs in the Dose Escalation portion will be tabulated by cancer type, dose level and in total for the DLT Evaluable Population. A listing of DLT events will also be provided.

#### 4.9.4 Analysis of AEs

Only TEAEs will be tabulated by system organ class or standard MedDRA query (SMQ) or high level term, and preferred term for the subjects in the Safety Population by cancer type and in total. Summary tabulations include the following:

- An overall summary of TEAEs.
- Grade 3 or higher TEAEs
- Drug-related TEAEs
- Grade 3 or higher drug-related TEAEs
- TEAEs with outcome of death
- Treatment-emergent serious AEs (SAEs)
- PEGPH20 related treatment-emergent SAEs
- Pembrolizumab related treatment-emergent SAEs
- TEAEs leading to discontinuation of study drug
- TEAEs related to PEGPH20 leading to discontinuation of PEGPH20
- TEAEs related to pembrolizumab leading to discontinuation of pembrolizumab
- Summary of Treatment-emergent thromboembolic events by standard MedDRA query (SMQ)
- Summary of Treatment-emergent serious thromboembolic events by SMQ
- Bleeding TEAEs by SMQ
- Musculoskeletal TEAEs by MedDRA high level term.

Subjects experiencing the same AE more than once will have that event counted only once within each body system, and once within each preferred term in all summary tabulations. Listings will be provided for AEs leading to death, SAEs, grade 3 and above AEs, and AEs leading to discontinuation of study drug. Additionally, by-subject listings of the AEs will be presented including, but not limited to, verbatim term, preferred term, system organ class, NCI-CTCAE grade, and relationship to study drug.

#### 4.9.5 Vital Signs and Body Weight

Vital signs assessments will be performed pre dose on Day 1, Day 8, and Day 15 of all cycles and at the End of Treatment visit. On all other days, vital signs will be evaluated for clinically significant AEs.

Vital signs including blood pressure (systolic and diastolic), heart rate (beats/min), respiratory rate (breaths/min), body temperature (°C) and weight (kg) will be summarized by visit and by cancer type and in total using descriptive statistics.

Height (cm), weight (kg) and body surface area (BSA; m^2) will be summarized by visit using descriptive statistics. BSA is calculated using DuBois formula as:

$$BSA = 0.007184 * W^{0.425} * H^{0.725}$$

By-subject listings of vital signs and body weight will also be provided.

#### 4.9.6 Clinical Laboratory Evaluation

Clinical laboratory evaluations will be performed at specified time points per schedule of study events in the protocol. All clinical laboratory evaluations will be performed by a central laboratory. In addition, local laboratories may be used if immediate clinical decision making is required. The following clinical laboratory tests will be performed:

- Hematology: Minimally, scheduled hematology collections should include hemoglobin, hematocrit, red blood cell count, white blood cell (WBC) count, neutrophils (ANC), lymphocytes (absolute), monocytes (absolute), eosinophils (absolute), basophils (absolute), granulocytes (absolute), mean corpuscular hemoglobin, mean corpuscular volume, and platelet count
- Serum electrolytes and chemistry: glucose, blood urea nitrogen (BUN), albumin, total bilirubin, alkaline phosphatase, AST, ALT, electrolytes (including sodium, potassium, calcium, magnesium, chloride, and bicarbonate), and creatinine
- Coagulation parameters: international normalized ratio (INR), prothrombin time (PT), and partial thromboplastin time (PTT)
- Thyroid function tests: free T3, free T4, and TSH
- Urinalysis: protein, glucose, ketones, blood, specific gravity, nitrite, pH, and leukocytes

All lab values will be reported and summarized by cancer type and in total using standard international (SI) units. Only central lab data for hematology, serum electrolytes and chemistry, coagulation, and thyroid function tests will be used for summarizing laboratory values by visit and change from baseline. All lab data for hematology, serum electrolytes and chemistry, and coagulation from both central and local labs will be used for summarizing lab parameters with worst CTCAE grade at post-baseline visits and their shift from Baseline. Laboratory results will be graded using NCI CTCAE V4.03, if applicable.

All clinical laboratory data will be listed, and values deemed clinically significant will be flagged. Frequency and percentage of subjects with laboratory values of ALT, AST, BILI, and ALP who meet Hy's law criteria (ALT >  $3 \times ULN$  or AST >  $3 \times ULN$ , BILI  $\ge 2 \times ULN$  and ALP <  $2 \times ULN$ ) at any time point will be summarized by cancer type and in total.

#### 4.9.7 12-Lead Electrocardiogram (ECG)

ECGs are taken at Screening, End of Treatment visit and as needed basis when clinically indicated. Frequency and percentage of subjects who had post-baseline abnormal (clinically significant or not clinically significant) ECG findings will be summarized by cancer type and in total.

A listing will be provided for the ECG data.

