 - b. **Dose Expansion portion -** Available tumor tissue in FFPE block or 10-15 unstained consecutive tumor tissue slides from 1 tumor tissue block that meet specific tissue sample requirements are mandatory. **Note:** Fine needle aspirates or brushing biopsies will not be acceptable. Archived resection specimens from the primary tumor without radiologic evidence of metastasis at the time of resection are not suitable to establish histological confirmation and require new tumor tissue of a metastatic site.
- 5. To be eligible for the Dose Escalation portion, subjects need only have evaluable disease (details in Section 8.2.15); to be eligible for the Dose Expansion portion, subjects must have measurable disease per RECIST v1.1. Previously irradiated tumors may be eligible if they have clearly progressed in size.
- 6. Eastern Cooperative Oncology Group (ECOG) Performance Status of 0 or 1 (Appendix B).
- 7. Life expectancy ≥ 3 months.
- 8. Males and females aged \geq 18 years.
- 9. Resolution of all acute toxic effects of prior therapy or surgery to baseline.
- 10. Screening clinical laboratory values are as follows:
 - a. Total and indirect bilirubin $\leq 1.5 \times$ upper limit of normal (ULN), except for Gilbert's syndrome
 - b. Aspartate aminotransferase (AST), alanine aminotransferase (ALT), and alkaline phosphatase (ALP) $\leq 2.5 \times \text{ULN}$ ($\leq 5 \times \text{ULN}$ is allowed if liver metastases are present)
 - c. Serum creatinine ≤1.5 mg/dL or calculated creatinine clearance ≥40 mL/min
 - d. Serum albumin >3.0 g/dL
 - e. Hemoglobin ≥10 g/dL (transfusion and erythropoietic agents allowed)
 - f. Absolute neutrophil count ≥1500 cells/mm³
 - g. Platelet count $\geq 100,000/\text{mm}^3$
- 11. Female participants of childbearing potential (WOCBP) must have a negative urine or serum pregnancy test within 7 days before Day 1 (first dose of study medication).
- 12. For WOCBP and for men, agreement to use an effective contraceptive method from the time of screening throughout the study until 4 months (WOCBP) or 3 months (men) after administration of the last dose of any study medication. Highly effective contraceptive methods consist of prior sterilization, intrauterine device (IUD), intrauterine hormone releasing system (IUS), oral or injectable contraceptives, and/or barrier methods. Abstinence alone is not considered an adequate contraceptive measure for the purposes of this study.

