11.1.8. Safety Analyses

All safety parameters will be summarized using the Safety Population by dose level will be descriptive in nature. No inferential statistical tests will be conducted for safety parameters.

All AEs will be presented in incidence tables coded by the Medical Dictionary for Regulatory Activities (MedDRA) Preferred Term and System Organ Class.

Additionally, separate AE incidence tables, coded by MedDRA term, will be presented by: 1) toxicity grade (severity) graded by the CTCAE and 2) relationship to study medication (PEGPH20 and pembrolizumab).

All AEs, SAEs, AEs leading to treatment discontinuation, and deaths occurring during the study will be summarized.

In addition, subjects who experienced TE will be summarized by SMQ term and MedDRA preferred term by grade.

Laboratory parameters and vital signs and the corresponding change from baseline over time will be summarized using descriptive statistics.

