#### Secondary:

- DOR, DCR and PFS based on RECIST v1.1, and OS.
- ORR, DOR, DCR, and PFS based on irRC.
- PK parameters of PEGPH20:  $C_{max}$ ,  $C_{min}$ ,  $T_{1/2}$ , AUC,  $V_D$  and CL.
- Incidence of AEs.
- Changes in clinical safety laboratory values.
- Changes in cardiovascular parameters (electrocardiogram [ECG]) and vital signs.

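### The secondary safety endpoint is change in ECG and vital signs, but the SAP's ECG count ignores the Screening tracing and its vital-sign tables omit the change from baseline that the protocol requires

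*SAP*

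**What the plan says.** Protocol 5.2.2 and SAP 4.3.2 list the same Dose Expansion secondary endpoint: "Changes in cardiovascular parameters (electrocardiogram [ECG]) and vital signs".

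**ECG.** SAP 4.9.7 gives the timing: "ECGs are taken at Screening, End of Treatment visit and as needed basis when clinically indicated". The planned summary, for each cancer type and overall, is "Frequency and percentage of subjects who had post-baseline abnormal (clinically significant or not clinically significant) ECG findings will be summarized". Beyond that there is only a by-subject display: "A listing will be provided for the ECG data". Protocol 11.1.8 describes no ECG analysis.

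**Vital signs.** Protocol 11.1.8 states: "Laboratory parameters and vital signs and the corresponding change from baseline over time will be summarized using descriptive statistics". SAP 4.9.5 says vital signs "will be summarized by visit and by cancer type and in total using descriptive statistics" and adds by-subject listings. It does not mention change from baseline.

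**Elsewhere in the SAP.** Section 4.1 defines baseline as the last non-missing value before any study drug. Section 4.9.6 plans change from baseline for laboratory values, and shift from baseline for worst CTCAE grade. Section 5 lists two changes from the protocol, the Tumor Response Evaluable Population and the use of local laboratory data; neither concerns vital signs. The Hy's law count in 4.9.6 covers subjects who meet the criteria "at any time point will be summarized by cancer type and in total".

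**The concern.** An endpoint worded as change needs an analysis that compares each subject after treatment with the same subject before it. The ECG summary makes no such comparison. A subject with the same minor abnormality at Screening and at End of Treatment enters the count, as does a subject whose normal tracing became clinically significantly abnormal. The resulting percentage is the prevalence of abnormal tracings in people with advanced cancer, and it mixes what they brought to the study with what arose during it.

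The study is single-arm, so there is no control group against which to read that prevalence. The subject's own baseline is the only internal comparator for these measures. Routine post-baseline ECGs are also sparse (End of Treatment, otherwise when clinically indicated), which makes pairing with the Screening tracing more useful.

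For vital signs the protocol asked for the paired quantity and the SAP dropped it without saying so.

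**Working it through.** There is no stated alpha, power or sample-size figure to reproduce. The check sets the sections side by side, with one illustration for scale.

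**1. ECG: endpoint against analysis.** The endpoint is change. The analysis counts subjects with at least one abnormal post-baseline tracing. The rule has no condition on Screening status, no shift table and no restriction to new or worsened findings. The Screening ECG is collected (protocol Table 1, SAP 4.9.7) and meets the SAP 4.1 definition of baseline, so the comparison is possible. Eligibility does not remove the issue: protocol 7.2 excludes pre-existing atrial fibrillation and NYHA Class III or IV disease, but not other ECG abnormalities.

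**2. ECG: direction and possible size.** Let b be the proportion abnormal at Screening, p the proportion of those still abnormal post-baseline, and i the proportion of Screening-normal subjects who become abnormal.

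- Proportion counted by the SAP rule = b × p + (1 − b) × i
- Newly abnormal, as a proportion of all subjects = (1 − b) × i
- Share of the count already abnormal at entry = b × p / [b × p + (1 − b) × i]

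The documents give none of these rates. Assumed ranges: b 10% to 40%, p 70% to 100%, i 5% to 10%.

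| b | p | i | SAP count | Newly abnormal | Share abnormal at entry |
|---|---|---|---|---|---|
| 10% | 70% | 5% | 7% + 4.5% = 11.5% | 4.5% | 7/11.5 = 61% |
| 10% | 70% | 10% | 7% + 9% = 16% | 9% | 7/16 = 44% |
| 20% | 100% | 5% | 20% + 4% = 24% | 4% | 20/24 = 83% |
| 40% | 100% | 5% | 40% + 3% = 43% | 3% | 40/43 = 93% |
| 40% | 100% | 10% | 40% + 6% = 46% | 6% | 40/46 = 87% |

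The shares do not depend on the number of subjects. For scale, SAP 4.7.2 reports 25 + 17 = 42 subjects enrolled in Dose Expansion, so the lowest and highest counts above are about 4.8 and 19.3 subjects. The newly abnormal column leaves out subjects who move from not clinically significant to clinically significant, which is also a change. The direction is certain for any subject whose Screening abnormality persists; the size is not known.

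**3. Vital signs: protocol against SAP.** Protocol 11.1.8 requires values and change from baseline over time. SAP 4.9.5 supplies values by visit. The visits include pre-dose Day 1 of every cycle, so Cycle 1 Day 1 pre-dose values are displayed; what is missing is the paired change. Subtracting one visit mean from another does not recover it once subjects leave:

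(mean at visit k, subjects remaining) − (baseline mean, all subjects) = (mean paired change, subjects remaining) + (baseline mean of subjects remaining − baseline mean of all subjects).

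The last term is the shift in case mix, and the SAP table cannot separate it from change. Because SAP 4.9.6 keeps change from baseline for laboratory values and Section 5 is silent on vital signs, this is an undeclared departure from the protocol.

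**4. Hy's law: a minor related point.** SAP 4.9.6 limits the worst-grade summary to post-baseline visits but not the Hy's law count. Inclusion criterion 10 (protocol 7.1) caps AST, ALT and ALP at 2.5 × ULN, but up to 5 × ULN "is allowed if liver metastases are present", and it exempts Gilbert's syndrome from the bilirubin limit of 1.5 × ULN. A pre-dose sample can therefore meet the aminotransferase element (>3 × ULN). Meeting the full criterion at entry would need liver metastases with ALT or AST >3 × ULN, Gilbert's syndrome with bilirubin ≥2 × ULN, and ALP <2 × ULN, all together. That is possible but would be rare.

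**The case against.** The strongest reply is that the information is not lost. ECG data and by-subject vital signs are listed, and 42 expansion subjects can be read through by hand. Protocol 10.2 counts worsening of a pre-existing condition as an adverse event, so a clinically important deterioration should reach the treatment-emergent tables in SAP 4.9.4. This stands in part: a reader might infer that the endpoint cannot be answered at all, and that would be too strong. But a listing is not a summary, and adverse event tables reflect what investigators chose to report rather than measured change.

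Second, the parenthesis in the ECG sentence could mean two reported categories rather than one pooled count. That reading is open. It would separate significant from non-significant findings, but would still not use the Screening result.

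Third, for ECG there is no departure from the protocol, since 11.1.8 specifies no ECG analysis. That is correct. The ECG gap is between endpoint and analysis; only the vital-sign gap is a departure.

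Fourth, safety analyses are descriptive, and no dose, stopping or efficacy decision is tied to these tables. That limits the seriousness. Nor would change from baseline cure informative dropout: it removes the shift in baseline mix, but still describes only those who remain.

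Fifth, for laboratory values the worst post-baseline CTCAE grade with shift from baseline already covers chemistry, so the Hy's law count is not the only view of liver tests. This stands, and is why that part is only a minor addition.

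**Conclusion.** The point holds, at modest weight. The single ECG summary does not measure change and counts unchanged entry abnormalities as post-baseline findings. The vital-sign summary lacks the change from baseline that the protocol requires, and the SAP does not declare this.

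Four stronger readings are not supported:

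- Vital signs are not summarised without any baseline; Cycle 1 Day 1 pre-dose values are in the by-visit display.
- Entry abnormalities in vital signs are not reported as on-treatment findings, because SAP 4.9.5 neither classifies nor counts vital-sign abnormalities. That consequence belongs to ECG.
- The 44% to 93% range is not an estimate for this trial. It rests wholly on the assumed rates and shows only that the effect could be large.
- The Hy's law count is not shown to be inflated in practice; a case at entry needs several uncommon conditions at once.

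**What to change.** - **SAP 4.9.7:** add a shift table from Screening (normal / abnormal not clinically significant / abnormal clinically significant) to the worst post-baseline category, by cancer type and in total, with a count of subjects who worsened.
- **SAP 4.9.5:** add change from baseline by visit, using the baseline definition in SAP 4.1, so that the SAP matches protocol 11.1.8. If the sponsor prefers not to, declare the omission in SAP Section 5.
- **SAP 4.9.6 (minor):** limit the Hy's law count to post-baseline samples, and show whether ALT or AST was already >3 × ULN at baseline.

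The cost is SAP wording and table shells. Screening ECGs, pre-dose vital signs and baseline laboratory values are already collected, so no extra assessment is needed.

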#### 4.10 ECOG Performance Status

Frequency and percentage of subjects in each ECOG performance status score will be displayed at baseline. Listings of ECOG will be provided.

#### 4.11 Immunogenicity Assessments

A blood sample will be collected from all subjects who receive PEGPH20 and analyzed to determine if PEGPH20 is eliciting a humoral immune response. Initial anti-drug antibodies (ADA) testing will be done using a multi-tiered approach per the Guidance, and immunocompetition will be performed to confirm an initial positive response in the screening assay. Any samples confirmed as positive in the ADA assay will then be assayed for neutralizing antibodies. ADA status (positive or negative) will be tabulated at each scheduled time point and overall at post-baseline for subjects receiving PEGPH20. Number and percent of subjects with positive neutralizing antibodies will be summarized descriptively at each scheduled time point and overall at post-baseline. For each subject, overall is defined as positive if at least one post-baseline neutralization test result is positive. A listing of the ADA data will also be provided.

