- ^h A confirmatory scan should be performed no sooner than 28 days after the initial scan that showed a response based on RECIST v1.1 (PR or CR) or irRC. A confirmatory scan should also be performed to confirm disease progression based on irRC no sooner than 28 days after the initial scan that showed progression.
- ¹ CT/MRI of the brain will be performed for the duration of the study (i.e., post-baseline), if clinically indicated, and within a target of 1 week after a subject achieves a complete response (CR). For NSCLC subjects with a history of treated brain metastases, brain scans will be performed at tumor assessment time points.
- ^j Optional PET/CT will be performed at selected sites. The CIV will analyze PET/CT scans if they are conducted.
- ^k Optional DCE-MRI will be performed at selected sites. The CIV will analyze PET/CT and DCE-MRI scans if they are conducted.
- ¹ On Days 1, 8, and 15 of Cycle 1 and Day 1 of Cycle 2, measurements of total bilirubin, ALP, AST, and ALT (as part of blood chemistry) must be obtained prior to dosing (within 48 hours is acceptable). Local laboratories may be used for these measurements. Dosing can only take place if total bilirubin, ALP, AST and ALT values are within the ranges specified in the Inclusion Criteria. If a subject has any of these values outside the specified ranges on Day 1 of Cycle 2, the Investigator should discuss further dosing plans for the subject with the Sponsor.
- m Blood samples will be collected for testing of thyroid hormones (free T3, free T4, and TSH]) on Day 1 of Cycle 2 and every third cycle thereafter (i.e., Day 1 of Cycles 2, 5, 8, 11, 14, 17, 20, etc.).
- ⁿ Plasma samples for PEGPH20 immunogenicity will be drawn prior to PEGPH20 dosing on day 1 of every cycle and end of treatment.
- Optional post-dose tumor biopsy should be done at the end of Cycle 1 (on or after Day 18) but prior to 1st PEGPH20 dose in Cycle 2.
- Piroxicam (20 mg) will be administered at least 1-2 hours prior to PEGPH20 administration on the day of dosing (timing will be at the Investigator's discretion based on the piroxicam manufacturer's Prescribing Information and subject's convenience), to minimize the severity of MSEs. Prophylactic use of a proton pump inhibitor is mandated for all subjects while receiving PEGPH20 (e.g. 20 mg omeprazole daily or over-the-counter [OTC] equivalent).

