## 4 STATISTICAL METHODS

#### 4.1 General Considerations

In general, continuous variables will be summarized using descriptive statistics (N, mean, standard deviation [SD], median, minimum [min], maximum [max], and quartiles). Categorical variables will be summarized using frequencies and percentages. In each summary table, figure or data listing, analysis population considered will be included in the title.

PEGPH20 and pembrolizumab are referred to as study drugs.

Study day 1 for a subject is defined as the first day that any study treatment is administered to the subject. The day before the study day 1 is referred to as study day -1. Unless otherwise indicated, the baseline value of a parameter is defined as the latest non-missing value taken prior to the administration of any study drug.

Statistical analyses will be performed and related outputs will be produced using the SAS® software Version 9.3 or higher. All tables, figures, and data listings will be independently checked for accuracy, consistency, and integrity in accordance with Medpace standard operating procedures or work instructions.

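### The SAP's overall post-baseline immunogenicity status has no baseline condition, so the overall rate cannot separate antibodies elicited by PEGPH20 from antibodies already present before dosing

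*SAP*

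**What the plan says.** SAP 4.11 states the purpose of the samples: they are "analyzed to determine if PEGPH20 is eliciting a humoral immune response". Protocol 8.2.14 gives the same purpose.

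Testing is tiered. A screening result is confirmed by immunocompetition, and then "Any samples confirmed as positive in the ADA assay will then be assayed for neutralizing antibodies".

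Two tabulations follow, plus a listing:

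- For antibodies of any kind: "ADA status (positive or negative) will be tabulated at each scheduled time point and overall at post-baseline for subjects receiving PEGPH20".
- For neutralizing antibodies: "Number and percent of subjects with positive neutralizing antibodies will be summarized descriptively at each scheduled time point and overall at post-baseline".
- At subject level: "A listing of the ADA data will also be provided".

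Directly after the neutralizing-antibody sentence comes the only rule for a subject's overall status: "overall is defined as positive if at least one post-baseline neutralization test result is positive".

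A pre-treatment sample exists. Protocol Section 3, Table 2, footnote n, says: "Plasma samples for PEGPH20 immunogenicity will be drawn prior to PEGPH20 dosing on day 1 of every cycle and end of treatment". That includes Cycle 1, and Table 3 shows the same pre-dose draw. SAP 4.1 has a general definition under which the "baseline value of a parameter is defined as the latest non-missing value taken prior to the administration of any study drug". SAP 4.11 does not use it in the overall rule.

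**The concern.** Whether a drug elicits antibodies is a question about change from the pre-treatment state. The overall rule looks only at what is found after baseline. A subject who carried antibodies before the first dose and shows the same finding later is overall positive, exactly like a subject who converted on treatment. Eligibility does not remove this possibility: the exclusion criteria in protocol 7.2 bar known allergy to hyaluronidase, but not antibody positivity at baseline.

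Other safety sections of the SAP do account for the pre-treatment state. Treatment-emergent adverse events are defined mainly by onset relative to first dose (4.9.1), and laboratory results are summarized as change and shift from baseline (4.9.6). Immunogenicity has no counterpart.

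There is a second, smaller gap. An overall post-baseline ADA status is to be tabulated, but the one sentence that defines overall refers to neutralization results. How to derive overall ADA status is left to the programmer.

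At stake is the interpretation of a descriptive safety rate: a reader could take it as the frequency of antibody formation on PEGPH20 when it is a post-baseline prevalence.

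**Working it through.** The documents state no immunogenicity rate, so there is no planned figure to reproduce. The check is a reading of the rule followed by simple algebra.

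**Step 1: apply the rule to each type of subject.** For one assay, with at least one evaluable sample before and after first dose:

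| Baseline | Any post-baseline positive | Overall status under the rule | Elicited on treatment? |
|---|---|---|---|
| Negative | No | Negative | No |
| Negative | Yes | Positive | Yes |
| Positive | No | Negative | No |
| Positive | Yes | Positive | Not shown; needs evidence of a rise |

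The second and fourth rows are pooled. Only the second answers the stated question.

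**Step 2: size of the pooling.** Let

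- p = proportion of subjects positive at baseline,
- r = proportion of those with at least one positive post-baseline result,
- b = p × r, the share of all subjects positive at baseline who stay positive,
- i = induction rate among baseline-negative subjects.

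Overall rate = b + (1 − p)i.
Induced share of all subjects = (1 − p)i.
Excess = b.

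The excess does not depend on i.

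**Step 3: illustration.** Neither document gives p, r or i, so the values here are assumptions. Take r = 1 (so b = p) and i = 10%, with all subjects as the common denominator:

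- p = 0%: overall 0 + 1.00 × 10% = 10.0%; induced share 10.0%; excess 0 points.
- p = 5%: overall 5% + 0.95 × 10% = 14.5%; induced share 9.5%; excess 5 points.
- p = 10%: overall 10% + 0.90 × 10% = 19.0%; induced share 9.0%; excess 10 points.

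If some baseline-positive subjects turn negative (r < 1), the excess is smaller than p.

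SAP 4.7.2 reports 25 gastric and 17 NSCLC subjects enrolled in Dose Expansion, 42 in total. If all were treated and sampled, the excess corresponds to 0, 42 × 0.05 = 2.1, or 42 × 0.10 = 4.2 subjects.

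**Step 4: which assay.** The neutralization assay is run only on confirmed ADA-positive samples, so neutralizing positivity cannot be more frequent than ADA positivity, at baseline or later. The b that applies to the written rule is the one for neutralizing antibodies, and it is no larger than the ADA baseline rate.

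**Step 5: can the other planned outputs supply the answer?** Cycle 1 Day 1 pre-dose is a scheduled time point, so the by-time-point tables will show how many subjects were positive at baseline. They are marginal counts and do not link a subject's baseline result to later results. The listing makes that link, but only if the reader builds the cross-classification by hand.

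**The case against.** The strongest defence is that the SAP does not mislabel anything. Section 4.11 never calls the overall figure induced or treatment-emergent. It is described as an overall post-baseline figure, and as a prevalence that is accurate. Baseline positivity is visible in the by-time-point tables and the listing. Immunogenicity is not among the listed endpoints for either portion, and no test, sample size or decision rule rests on it. All of this stands and limits the importance of the point. It does not remove the mismatch between the section's stated aim and its only subject-level rule.

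A reader might go further and infer that the rule discards non-neutralizing antibodies, so that every ADA-positive, neutralization-negative subject is lost. The text does not support that. The rule follows the neutralizing-antibody sentence and is most naturally read as governing that summary alone, while ADA status of any kind is tabulated separately. Even if the sentence were applied to both summaries, ADA results would still appear at each time point and in the listing. What remains is that the overall ADA rule is unwritten. Most programmers would probably take any positive post-baseline ADA result.

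A reader might also infer that the error could run in either direction. That depends on the same misreading. With it set aside, the only effect relative to the induced share is upward.

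**Conclusion.** The point holds in limited form. The overall rule cannot by itself show whether PEGPH20 elicited an antibody response, because it counts subjects already positive before dosing who remain positive. The excess over the induced share of all subjects equals their proportion exactly. That proportion is not in the documents. If it is 0% there is no excess; the figures of 5 and 10 points are illustrations, not estimates. The rule for overall ADA status is not explicitly stated.

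The documents do not support the inference that the SAP reports pre-existing antibodies under the name of induced ones, or that this rate is the leading immunogenicity result: the SAP gives it no priority over the rates by time point. Because the summary is descriptive, the primary ORR tests and all efficacy conclusions are untouched. This is a free improvement, not a flaw that threatens the trial.

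**What to change.** In SAP 4.11:

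1. Define overall ADA status from confirmed ADA results and overall neutralizing status from neutralization results, each in its own sentence. State that a sample negative in the ADA assay counts as neutralization-negative, since it is not run in the second assay.
2. For each status, add a treatment-induced rate. The numerator is subjects negative at baseline with at least one positive post-baseline result. The denominator is baseline-negative subjects with evaluable baseline and post-baseline samples. Use the baseline definition already in SAP 4.1.
3. Report baseline-positive subjects separately, classified as boosted where titres are available.
4. Keep the planned overall figure if wanted, labelled as post-baseline prevalence.

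The cost is a few lines of SAP text and one additional table program. The pre-dose Cycle 1 Day 1 sample is already scheduled, so no new samples or visits are needed.
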